			8.2.1 Description of patients
			• Editorial revisions in the part "Combination clinical
			practice"
			• Added a statement about patients after data linkage
			in the part "Constitution".
			• Corrected the analysis set used and time categories
			in the part "Discontinuation and dropouts".
			8.2.2 Patient characteristics and treatment history
			Editorial revisions
			• Added factors for the analysis of patient
			characteristics.
			• In the part "Exposure of this drug", revised the
			definition of duration of treatment and added the item
			total number of treatment weeks.
			8.2.3.1 Adverse reactions
			• Added a summarization plan for selected adverse
			reactions.
			• Editorial revisions in "Major investigation items"
			
 
Modified the categorization of onset timing in
 

			"Onset timing of adverse reactions"
			• Deleted the statement specific to loperamide in
			"Association between concomitant medication and
			adverse reactions".
			8.2.3.1 Adverse events
			• Added analysis plans of presenting a tabulated list
			of deaths and summarizing SAEs by seriousness.
			• Added a plan of summarizing AEs leading to
			discontinuation.

Version	Date	Author(s)	Summary of Changes/Comments
			8.2.3.2 Subgroup analyses
			• Added a statement about risk ratio.
			• Editorial revisions in the statement on
			hepatotoxicity
			• Modifications in the summarization plan for liver
			transplantation and infections
			Added a plan to perform subgroup analyses
			concerning patients with special characteristics.
			8.2.3.3 TTR amyloidosis-related symptoms other than
			peripheral neuropathy
			• Added this subsection.
			8.2.4.1 Time variations in NIS scores
			• Added plans regarding summarization at each time
			point, analysis of variance, and box plotting.
			8.2.4.2 Time variations in QOL-DN
			• Added plans regarding summarization at each time
			point, analysis of variance, and box plotting.
			8.2.4.3 Time variations in mBMI
			Correction of printing errors
			8.2.4.6 Survival analysis
			• Added this subsection.
			8.2.4.7 Subgroup analyses
			• Added TQOL as an analysis item.
			• Added a plan to summarize scores at each time
			point.
			Added a supplementary sentence concerning
			pretreatments and concomitant medications.
			CCI
			CCI
			9 LISTINGS
			• Updated the set of listing items to include mutant
			genotypes, deaths, pregnant women, non-target
			diseases, and liver transplantation.

Version	Date	Author(s)	Summary of Changes/Comments
			10.1 Appendix 1: Details of Data Extraction
			Modifications in visit timing; editorial revisions
			Other
			Editorial revisions
3.0	25-Apr-2018	PPD	5.4. Subgroups
			• "Patient characteristics": Added "Body weight".
			• "Patient characteristics": Deleted "Mutant genotype
			1".
			• "Patient characteristics": Modified the plan
			regarding past history of liver transplantation.
			6.1. Safety Endpoints
			• "Adverse reactions": Deleted "Adverse reactions as
			assessed by company".
			Added "Serious adverse events or serious adverse
			reactions"
			8.2.2. Patient characteristics and treatment history
			• "Patient characteristics": Added "Body weight" and
			"History of pregnancy during study period"
			• "Patient characteristics": Editorial revisions in the
			categorization of target diseases
			• "Patient characteristics": Modified the
			categorization for "Mutant genotype 1"
			• "Patient characteristics": Added the analysis item
			"Disposition of non-V30M mutations"
			• "Patient characteristics": Editorial revisions in the
			categorization for "Past history of liver
			transplantation"
			• "Patient characteristics": Editorial revisions and
			an addition in the categorization for "Timing of
			liver transplantation"
			8.2.3.3. TTR amyloidosis-related symptoms other
			than peripheral neuropathy
			Modifications in the analysis plan
4.0	18-Feb-2019	PPD	8.2.1 Description of patients
			• Updated the procedure to identify possible patients
			with combination clinical practice to include "mutant
			genotype" and "names of sites after patient transfer"
			as information to be considered; and modified a
			statement so that it reads that the identification will be
			determined at a case conference.

Version	Date	Author(s)	Summary of Changes/Comments
5.0	03-Oct-2019	PPD	6.1. Safety Endpoints, and 6.3. Other Endpoints
			• Integrated the part "TTR amyloidosis-related
			symptoms other than peripheral neuropathy" in
			Section 6.1 to the part "Medical assessments of
			physical symptoms" in Section 6.3 as an editorial
			revision.
			Addition of "8.1.5. Time data".
			8.2.1. Description of patients
			• Added the summarization plan for patients who
			complete the study period.
			8.2.2 Patient characteristics and treatment history, and
			8.2.3.1 Adverse reactions
			• Divided the time category "
			" $\geq$ 52 to <78 weeks" and " $\geq$ 78 to <104 weeks" in the
			analysis plans of duration of treatment in "8.2.2
			Exposure of this drug" and onset timing of adverse
			reactions in "8.2.3.1 Adverse reactions".
			8.2.3. Safety analysis, 8.2.5. Other analyses, and 10.1
			Appendix 1
			• Moved the content of "TTR amyloidosis-related
			symptoms other than peripheral neuropathy" in
			Section 8.2.3 to Section 8.2.5 with a change of
			analysis plan to that based on cross-classification
			after modifications in survival analysis and time
			points for the summarization.
			• In association with the above, deleted the definition
			of time points in A1.4, Section 10.1, and added
			medical assessments of physical symptoms to the set
			of endpoints defined in A1.1.
			8.2.4.6. Evaluation of survival time
			• Editorial revisions in association with the addition
			of Section 8.1.5
			Added "10.3.1. Analysis of interval censored data".
			Other
			• Editorial revisions
6.0	13-May-2020	PPD	5.4. Subgroups, 8.2.2. Patient characteristics and
			treatment history and 8.2.3.3. Subgroup analyses
			• Integrated different age categorizations to a single
			one.

Version	Date	Author(s)	Summary of Changes/Comments
			8.2.1. Description of patients
			• Deleted the plan to summarize studied sites and
			patients by type of site establisher. (This
			summarization had been included as data required
			for re-examination but became no longer needed.)
			8.2.2. Patient characteristics and treatment history
			• Changed the analysis sets used for the analyses of
			disposition of non-V30M mutations and method of
			diagnosis of FAP to the SAS alone.
			5.4. Subgroups
			Added a categorization for concomitant
			medications and pretreatments.
			8.2.3.1. Adverse reactions
			• Added a statement that important potential risks
			will be summarized by making a tabulated list of
			events (instead of in terms of n and proportion) if n
			is very small for each event.
			8.2.4.1. Time course of NIS and 8.2.4.2. Time course
			of QOL-DN
			CCI
			9. Listings
			• Deleted "Patients with AEs" and "Patients with
			SAEs" from the set of listing items; and made
			editorial revisions concerning Attachment Forms.
			Other: Editorial revisions
7.0	21-Oct-2020	PPD	5.2. Efficacy Analysis Set
			• Deleted the plan of the efficacy analysis in patients
			with non-target disease because this analysis is
			unnecessary.

Version	Date	Author(s)	Summary of Changes/Comments
			8.2.2. Patient characteristics and treatment history
			• Deleted "Mutant genotype 2", a factor that had been
			included in the factors for which summarization
			will be performed, because the summarization for
			this factor can be covered by that for "Mutant
			genotype 1".
			8.2.3.1. Adverse reactions
			• Added a statement that summarization for
			pre-specified events will be separately performed,
			as necessary, because it will be covered by the
			tabulation for all adverse reactions.
			8.2.4.6. Evaluation of survival time
			• For the determination of survival rate at specified
			time points performed in align with plotting of
			Kaplan-Meier's curve, changed the time points to
			those determined by considering each evaluation
			period.
			9. Listings
			• Like in Section 5.2, deleted "Results of efficacy
			evaluation in patients with non-target disease" from
			the set of listing items, because it is unnecessary.
8.0	07-May-2021	PPD	8.2.1. Description of patients
			Modified the categorization of the timing of last
			visit used for the summarization described in
			"Discontinuation and dropouts" to " $<52$ weeks, $\ge 52$
			to $<78$ weeks, $\geq 78$ to $<104$ weeks, $\geq 104$ to $<156$
			weeks" and explicitly stated that patients who
			complete the study period of this study will not be
			included in this summarization.
			8.2.2. Patient characteristics and treatment history
			• Changed the categorization of "Duration of
			treatment" in "Exposure of this drug" to "<52
			weeks, $\geq 52$ to $<78$ weeks, $\geq 78$ to $<104$ weeks, $\geq 104$
			to <156 weeks, ≥156 weeks".
9.0	21-April-2022	PPD	CCI

Version	Date	Author(s)	Summary of Changes/Comments
			10.3.2. Analysis of repeated measures data
			• Added a sample SAS code to show how the percent
			change described in Section 8.2.4.8 will be
			calculated.
			Other: Minor corrections
			• Made a terminological change from "study period"
			to "observation period".
			• In "Evaluation of survival time", Section 6.2,
			clarified the explanation of when survival will be
			determined.
10.0	13-Mar-2023	PPD	5.4. Subgroups
			• Changed the reference category for pretreatments
			and concomitant medications to "absent".
			• Identified the pretreatments and concomitant
			medications for which subgroup analysis will be
			performed.
			6.1. Safety Endpoints
			• Amended the name of the document referred to to
			identify the events covered by each major
			investigation item, in accordance with the name of the
			document submitted to PMDA.
			6.2. Efficacy Endpoints
			• In "Evaluation of survival time", added the
			definition of FAP-related death.
			• In "Evaluation of survival time", deleted "Time
			from birthdate to event" from the set of items
			evaluated as time to event.
			7. HANDLING OF MISSING DATA
			• In "Evaluation of Survival Time", added how to
			handle cases in which cause of death is missing.
			8.2.1. Description of patients
			• In "Constitution", added a summarization plan by
			planned observation time (Weeks 78 and 156).
			• Deleted the plan of summarizing the patients who
			complete the study period.
			8.2.2. Patient characteristics and treatment history
			•In "Other", added what period data of concomitant
			medications, concomitant non-drug therapies, and
			pretreatments will be collected; and added definition
			of past medical history and complications.

Version	Date	Author(s)	Summary of Changes/Comments
			8.2.3.1. Adverse reactions
			• In "Onset timing of adverse reactions", added
			definition of the denominator to calculate the
			proportion of patients with an adverse reaction.
			8.2.3.3. Subgroup analyses
			• Deleted the statement "risk ratio and its confidence
			interval will not be calculated for pretreatments and
			concomitant medications".
			8.2.4.6. Evaluation of survival time
			• Deleted the statement about "time from birthdate to
			event".
			CCI
			8.2.6.1. Measurement of plasma concentration of
			tafamidis in patients with severe hepatic impairment
			• Added in what condition plasma concentrations of
			tafamidis will be tabulated.
			9. LISTINGS
			Added "Efficacy endpoints" and "Medical
			assessments of physical symptoms" to the set of
			listing items.
			CCI
			Other
			Editorial revisions

## 2. INTRODUCTION

This document describes the statistical analysis plan for the non-interventional study entitled "Vyndaqel Capsules Special Investigation - Investigation on long-term use -". In this SAP, citations from the corresponding protocol are indicated in *italics*.

## 2.1. Study design

Target patients

All patients who received/used this drug will be targeted in this study.

Dosage and administration

The usual adult dosage for oral use is 20 mg of tafamidis meglumine once daily.

Observation period

3 years from the first day of treatment with this drug (156 weeks)

However, the observation period for patients who started to receive this drug after May 2018 will be 1.5 years (78 weeks).

Major investigation items

Hepatotoxicity should be evaluated in this study as a major investigation item and, if information on hepatotoxicity is obtained, it will be separately investigated in detail.

[Rationale for setting]

Although necrosis and hypertrophy of hepatocytes were observed in the repeated-dose toxicity study in mice, since the Japanese clinical data at the time of approval application are limited, hepatotoxicity was set as the major investigation item in this study to confirm the post-marketing safety profile.

Study size and its rationale

[Planned sample size]

All patients who received/used this drug will be targeted in this study.

## [Rationale for sample size]

On the basis of the review of data on patients with familial amyloid polyneuropathy who were registered in the database from the Amyloidosis Clinical Survey Forms of the Specific Diseases Treatment Research Program by the Ministry of Health, Labour and Welfare for 3 years from 2003 to 2005, it is reported that the number of patients with familial amyloid polyneuropathy is 64 to 88 patients/year, and the estimated prevalence of familial amyloid polyneuropathy in Japan is 0.87 to 1.1 per population of 1 million people after the number of patients was corrected and calculated from the acquisition rate of data 1). When this

> PFIZER CONFIDENTIAL Page 13

prevalence is multiplied by the Japanese population (127.54 million, as of November 2012), the estimated number of patients with TTR-FAP (hereinafter referred to as this disease) is approximately 111 to 140. On the website of the Japan Intractable Diseases Information Center, the estimated annual number of patients treated for this disease is approximately 130 on the basis of the nationwide epidemiological survey conducted in 1991. As described above, considering that this disease is a rare disease and the safety and efficacy information of this drug based on Japanese clinical studies are limited, all patients who received/used this drug will be collected as much as possible.

Planned period covered by this study

Duration of study: November 2013 to May 2021 (7.5 years)

Registration period: November 2013 to November 2019 (6 years)

A contract will be concluded after the start date of the study period, and then, the patient registration will be started.

## 2.2. Research Objectives

To understand information on the safety (e.g., onset status of adverse reactions) and efficacy of this drug in the long-term use under the post-marketing actual use in all patients receiving this drug.

Review on the onset status of hepatotoxicity will be set as a major investigation item in this study.

## **3. INTERIM AND FINAL ANALYSES**

In this study, interim analyses for the purpose of Japan Periodic Safety Update Report (J-PSUR) will be conducted on a regular basis. For an interim analysis, only necessary items selected from the full analysis items defined in this SAP will be analyzed. A final analysis will be conducted to support the application of reexamination. For the final analysis, the full items defined in this SAP will be analyzed.

#### 4. HYPOTHESES AND DECISION RULES

#### 4.1. Statistical Hypotheses

Not applicable.

#### 4.2. Statistical Decision Rules

Not applicable.

#### 5. ANALYSIS SETS

#### 5.1. Safety Analysis Set

Safety analysis will be performed using the safety analysis set (SAS) that consists of all registered patients who had their CRF collected and received at least one dose of this drug.

Patients who meet any of the criteria below, however, should be excluded from the SAS:

- Contract deficiency
- Contract violation
- Contract withdrawal
- Registration violation
- No information recorded on adverse events (Patients who had no record or made no visit even after reinvestigation was conducted because there was no record of AEs or of lack of AEs)

Although patients will not be excluded from the SAS just because reinvestigation could not be conducted, patients whose all records concerning administration of this drug or safety information could not be reinvestigated will be excluded from the SAS according to the criterion above.

Patients with iatrogenic TTR-FAP in whom TTR-FAP developed after liver transplantation from a donor with TTR-FAP (domino liver transplantation) will be included in this study. Patients registered for a non-target disease (e.g., cardiac amyloidosis) will also be included in the SAS.

## 5.2. Efficacy Analysis Set

The efficacy analysis set consists of all patients in the SAS in whom at least one of the efficacy endpoints below was evaluated. Patients registered for a non-target disease (e.g., cardiac amyloidosis) will not be included in the efficacy analysis set.

Efficacy endpoints: Neuropathy impairment score (NIS), Norfolk Quality of Life - Diabetic neuropathy (QOL-DN), modified body mass index (mBMI), ambulatory status (walking ability score used in polyneuropathy dysfunction rating scale), neurological assessment scores, and survival time

#### 5.3. Other Analysis Sets

The pharmacokinetics analysis set consists of all patients in the SAS in whom plasma concentration of tafamidis was measured.

#### 5.4. Subgroups

Subgroup analyses for safety and efficacy will be performed with respect to the following factors:

- Patient characteristics
  - Sex [male, female]
  - Age [ $<15 \text{ yrs.}, \ge 15 \text{ to } <65 \text{ yrs.}, \ge 65 \text{ yrs.}$ ]
  - Body weight [ $\leq 50 \text{ kg}$ ,  $\geq 50 \text{ to } \leq 60 \text{ kg}$ ,  $\geq 60 \text{ kg}$ ]
  - BMI [<18.5, ≥18.5 to <25.0, ≥25]
  - Onset age [ $\leq 50$  yrs.]  $\geq 50$  yrs.]
  - Duration of disease [ $\leq 5$  yrs.]  $\geq 5$  yrs.]
  - Past treatment with this drug [present, absent]
  - Mutant genotype 2 [with V30M, without V30M]

- Karnofsky performance status [100-80, 70-50, 40-10]
- Family history of TTR-FAP [present, absent]
- Origin of patient [endemic region, non-endemic region]
- Past history of organ transplantation [present, absent]
- Past history of liver transplantation (including for purposes other than the treatment of target disease) [present (including domino liver transplantation), absent] \* Only for safety assessment
- Past history of liver transplantation other than domino liver transplantation [present, absent (including domino liver transplantation)] \* Only for efficacy assessment
- Hepatic impairment [present, absent]
- Hepatic impairment [absent, mild, moderate, severe]
- Renal impairment [present, absent]
- Baseline total NIS score [ $\leq 70$ ,  $\geq 70$ ]
- Baseline NIS-LL score [ $\leq 10$ , >10 to  $\leq 20$ , >20]
- Baseline total QOL (TQOL) score [ $\leq 20$ , >20 to  $\leq 40$ , >40]
- Severity of disease [Stage 1 (walking ability score 0-2), Stage 2 (walking ability score 3a/3b),
   Stage 3 (walking ability score 4)]

Subgroup analysis for mutant genotype will be performed only in patients with a diagnosis of mutant genotype.

- Others
  - Pretreatment (loperamide) [present, absent]
  - Pretreatment (prednisolone) [present, absent]
  - Pretreatment (rosuvastatin) [present, absent]
  - Pretreatment (NSAIDs) [present, absent]
  - Duration of treatment [ $\leq 52$  weeks, >52 to  $\leq 104$  weeks, >104 to  $\leq 156$  weeks, >156 weeks]
  - Concomitant medication (loperamide) [present, absent]
  - Concomitant medication (prednisolone) [present, absent]
  - Concomitant medication (rosuvastatin) [present, absent]
  - Concomitant medication (NSAIDs) [present, absent]

## 6. ENDPOINTS AND COVARIATES

#### 6.1. Safety Endpoints

- Adverse reactions: AEs related or possibly related to this drug as assessed by the treating physician
- Adverse events
  - All-causality AEs
- Serious adverse events (SAEs) or serious adverse reactions: AEs or adverse reactions considered by the treating physician to be serious

- Major investigation items: Major investigation items include:
  - Hepatotoxicity

Events covered by each major investigation item will be identified according to the latest version of the separately prepared document, Rationale for Setting the Safety Specification Based on Risk Management Plan and Defined Events.

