7.3.2.12. Adverse events

Occurrence of adverse events (AEs) from the start date of administration of this drug to the end date of observation period should be confirmed and the following information should be recorded. If any AE is

observed, the investigator will take appropriate measures, promptly report it to Pfizer, and in principle, transcribe and confirm the course until the symptom disappears.

Also, further investigation should be separately conducted, if deemed necessary by Sponsor for patients who experienced a serious adverse reaction, an unexpected adverse reaction or other adverse reactions not listed in the package insert.

- (1) Presence/absence of AE
- (2) Name of AE
- (3) Date of occurrence
- (4) Intervention
- (5) Seriousness
- (6) Outcome
- (7) Causal relationship to this drug

If the AE is associated with abnormal laboratory values, i.e., clinical laboratory tests, the following information should also be recorded:

- (1) Laboratory parameter
- (2) Site reference value
- (3) Unit
- (4) Date measured
- (5) Results

Note: AEs are any and all unfavorable events (including clinically significant abnormal changes in laboratory tests) occurring in patients after starting the targeted drug treatment regardless of their causal relationship. Serious adverse events (SAEs) are any unfavorable medical occurrences that result in death, are life-threatening, require (or prolong) hospitalization, cause persistent or significant disability/incapacity, result in congenital anomalies or birth defects, or are other conditions which represent significant health hazards.

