7.7. Data analysis

1. Definition of analysis set

The safety analysis set (SAS) consists of all patients who received this drug at least once. The effectiveness analysis set consists of those for whom the effectiveness evaluation was conducted at least once among the SAS. The details will be described in the separately prescribed Statistical Analysis Plan (SAP).

2. Method of analysis

(1) Major analysis for safety evaluation

The occurrence of ADRs and the incidence of ADRs (percentage of patients with AEs for which the causal relationship with this drug cannot be ruled out) will be calculated in the SAS.

(2) Major analysis for effectiveness evaluation

For NIS, QOL-DN, and mBMI, their values and changes from baseline at each time point will be calculated in the effectiveness evaluation set. For ambulatory status, motor function (MRC), tendon reflex, tactile sense, pain sensation, vibration sense, and positional sense, changes from baseline at each time point will be calculated. In addition, survival time analysis will be performed using survival information obtained up to 3 years after the start of treatment.

Detailed methodology for summary and statistical analyses of data collected in this study will be documented in a SAP, which will be dated, filed and maintained by Pfizer. The SAP may modify the plans outlined in the protocol; any major modifications of primary endpoint definitions or their analyses would be reflected in a protocol amendment.

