9.3. Causality assessment

The investigator is required to assess and record the causal relationship. For all AEs, sufficient information should be obtained by the investigator to determine the causality of each AE. For AEs with a causal relationship to Vyndaqel, follow-up by the investigator is required until the event and/or its sequelae resolve or stabilize at a level acceptable to the investigator, and Pfizer concurs with that assessment.

An investigator's causality assessment is the determination of whether there exists a reasonable possibility that vyndaqel caused or contributed to an AE. If the investigator's final determination of causality is "unknown" and she/he cannot determine whether Vyndaqel caused the event, the safety event must be reported within 24 hours.

If the investigator cannot determine the etiology of the event but she/he determines that Vyndaqel did not cause the event, this should be clearly documented on the CRF and the NIS AEM Report Form.

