#### 7. HANDLING OF MISSING DATA

Adverse Events

If the severity of, action taken for, or outcome of an AE is missing, their value will be considered "unknown" for data summarizations.

– NIS

If the evaluation result for the right or left side on the same day is missing, the value for the evaluated side will be adopted as the score for the item.

– QOL-DN

If the score of an item included in the Physical Function/Large Nerve Fiber Disorder subscale, Activities of Daily Living subscale, Symptoms subscale, Small Nerve Fiber Disorder subscale, or Autonomic Neuropathy subscale is missing, the missing score will be imputed with the mean score from the evaluated items in the relevant subscale as long as  $\geq 60\%$  of the items in the subscale have been evaluated. The score for the subscale will be determined by summing the scores for the evaluated and imputed items.

The TQOL score will be determined by summing the scores for the evaluated and imputed items if all the 35 items have been evaluated or all missing values imputed by using the aforementioned method. If imputation could not be done by the aforementioned method for some items because of failure of evaluation for  $\geq 60\%$  of all items in a subscale, the TQOL score will be determined as 35 times the mean from the evaluated and imputed items, provided that at least 60% of all items have been evaluated or imputed. If  $\geq 40\%$  of the items in a subscale or the TQOL score are missing, the score for the subscale and the TQOL score will be treated as missing values.

Neurological Assessment

If the item toe extension and/or toe flexion in the motor domain have been evaluated and the results are directed to normal, other items in the same domain will be imputed with those directed to normal. If the item triceps surae in the reflexes domain has been evaluated and the result is normal, other items in the same domain will be imputed with normal. If the item toe in the light touch, pin prick, vibration, or position sense domain has been evaluated and the result is normal, other items in the same domain will be imputed with normal.

- Evaluation of Survival Time

If the cause of death is missing in the record of a death-confirmed patient, the patient will be treated as having died for unknown cause.

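### The SAP words the adverse-reaction definition differently from the protocol and has no rule for AEs whose causality is unknown or missing

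*SAP*

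**What the plan says.** - **Protocol 7.7 (Data analysis)** makes the occurrence and incidence of adverse reactions the major safety analysis. It defines the incidence as the "percentage of patients with AEs for which the causal relationship with this drug cannot be ruled out".
- **SAP 6.1 (Safety Endpoints)** defines adverse reactions as "AEs related or possibly related to this drug as assessed by the treating physician".
- **Protocol 9.3 (Causality assessment)** asks the investigator whether there is a "reasonable possibility that vyndaqel caused or contributed to an AE". It allows a final answer of *unknown*: where "she/he cannot determine whether Vyndaqel caused the event, the safety event must be reported within 24 hours". A separate sentence deals with the investigator who cannot find the etiology but does conclude that the drug was not the cause.
- **Protocol 7.3.2.12 (Adverse events)** lists the CRF item only as "Causal relationship to this drug". Its response categories are not given.
- **SAP Section 7 (Handling of Missing Data)** has one rule for AEs, which begins "If the severity of, action taken for, or outcome of an AE is missing" and sets those three fields to unknown. It does not mention causality.
- **SAP 8.2.3.2 (Adverse events)** tabulates all AEs regardless of causality, and tabulates serious and non-serious AEs by causal relationship.

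**The concern.** Causality decides whether an AE enters the adverse-reaction endpoint at all. The protocol admits everything except events judged unrelated. The SAP admits only events the physician has positively placed in one of two related categories. An AE rated *unknown*, or left blank, has not been excluded, so it meets the protocol definition. It has not been assessed as related or possibly so, so on a literal reading it fails the SAP definition.

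The SAP definition feeds overall reactions, serious reactions, their breakdown by action and outcome, onset timing (all 8.2.3.1) and the subgroup risk ratios (8.2.3.3). SAP 8.2.3.1 itself expects that counts for some important potential risks may be very small, and there one or two reclassified patients would be noticeable. Two programmers working from these documents could classify the same event differently.

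**Working it through.** No figure in the plan depends on this point, so the check is mainly a comparison of text.

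**Step 1. Classify each possible causality answer under both definitions, read literally.**

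| Physician's answer | Protocol 7.7 | SAP 6.1 |
|---|---|---|
| Related | reaction | reaction |
| Possibly related | reaction | reaction |
| Unknown | reaction (not excluded) | not counted |
| Blank | reaction (not excluded) | not counted |
| Not related | not a reaction | not a reaction |

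The definitions agree on three rows and differ on two.

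**Step 2. Can the two differing rows occur?** *Unknown* is foreseen in Protocol 9.3 and is kept apart there from a conclusion that the drug was not the cause, so the protocol does not equate the two. Blanks are possible: the study takes its data from medical charts, includes a retrospective survey (Protocol 7.2.3.1), and names missing information as a limitation (Protocol 7.9).

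**Step 3. Does another SAP rule settle them?** Section 7 covers severity, action taken and outcome only. The known/unknown split in SAP 8.2.3.1 classifies events already counted as reactions, so it does not help. Section 6.1 relies on the treating physician alone, so no second assessment is specified.

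**Step 4. Size.** Let N be the number of patients, x those with at least one AE rated related or possibly so, and k those whose only candidate event has unknown or missing causality.

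- Literal SAP incidence = x/N
- Protocol incidence = (x + k)/N
- Difference = k/N, whatever x is

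The documents give neither x nor k. For N, the sample-size rationale (Protocol 7.5.2, SAP 2.1) estimates 111 to 140 patients. This reproduces: 0.87 × 127.54 = 110.96 and 1.1 × 127.54 = 140.29. These are prevalence estimates, used here only as denominators. Assume x/N of about 20% and k/N of 0, about 2%, 5% and 10%; intervals are exact 95% limits.

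| N | x | k | Literal SAP | Protocol |
|---|---|---|---|---|
| 140 | 28 | 0 | 20.0% (13.7–27.6) | 20.0% (13.7–27.6) |
| 140 | 28 | 3 | 20.0% | 31/140 = 22.1% (15.6–29.9) |
| 140 | 28 | 7 | 20.0% | 35/140 = 25.0% (18.1–33.0) |
| 140 | 28 | 14 | 20.0% | 42/140 = 30.0% (22.6–38.3) |
| 111 | 22 | 0 | 19.8% (12.9–28.5) | 19.8% (12.9–28.5) |
| 111 | 22 | 2 | 19.8% | 24/111 = 21.6% (14.4–30.4) |
| 111 | 22 | 6 | 19.8% | 28/111 = 25.2% (17.5–34.4) |
| 111 | 22 | 11 | 19.8% | 33/111 = 29.7% (21.4–39.1) |

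**The case against.** The strongest reply is that the two wordings express one standard. An event whose link to the drug has not been excluded is ordinarily one that is possibly linked, and Protocol 9.3 frames the judgement as a reasonable possibility. If sites use the possible category for everything not excluded, or if the CRF offers only related and not related, the two sets are identical. The only source for *unknown* is a section on expedited reporting, not on analysis. Blanks are also guarded against: Protocol 9.3 requires causality to be recorded, and CRFs are queried (7.6.5.2) and checked for gaps before signature (7.6.5.3).

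Much of this stands. The CRF categories are not shown, the effect may be zero, and nothing suggests that blanks will be common. It does not remove the mismatch, because the SAP neither adopts the protocol wording nor says that *unknown* is folded into the possible category.

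Three stronger readings are tempting, and the documents do not support them:

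- A reader might infer that the SAP excludes these events by rule. It does not. Their exclusion follows from a literal reading of 6.1, and no sentence states it.
- A reader might infer that such events vanish from the safety report. They remain in the all-causality table and in the tables by causal relationship (SAP 8.2.3.2).
- A reader might infer that the hepatotoxicity count is affected. This is not clear-cut. SAP 6.1 identifies hepatotoxicity from a separate document of defined events, with no causality condition. SAP 8.2.3.1 counts patients with relevant events, although under the adverse-reactions heading. SAP Section 9 lists events and adverse reactions for the major investigation item separately.

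**Conclusion.** The point holds as a conflict between two stated definitions of the protocol's major safety measure, together with a missing classification rule. On a literal reading the SAP would count fewer events than the protocol, and the loss would be confined to the adverse-reaction analyses. Its size cannot be derived from the documents. In percentage points it is the share of patients whose only candidate event has unknown or missing causality: about 2, 5 or 10 points under the assumed shares above, and zero if there are no such patients. The assumed 20% incidence serves only as illustration.

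Protocol 7.7 lets the SAP modify its plans but sends major changes to primary endpoint definitions to a protocol amendment. The documents do not label this a primary endpoint, and the SAP may have intended no change, so a breach of that rule is not established.

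**What to change.** 1. In SAP 6.1, restate the protocol definition: an adverse reaction is any AE except one the treating physician has assessed as not related to the drug.
2. In SAP Section 7, add causality to the AE rule: unknown or missing causality counts as not excluded, so the event is counted as an adverse reaction.
3. Report the number of AEs with unknown or missing causality, and the number of patients who enter the incidence only because of them.

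If a narrower set is intended, the SAP should say that it departs from Protocol 7.7 and why. If the CRF allows only two answers, one sentence saying so would show that *unknown* cannot arise there.

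The cost is two or three sentences and one extra count, with no new data collection. The downside is that the reported reaction rate may be slightly less favourable.
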